### 12.3 CTEP Multicenter Guidelines

N/A

### 12.4 Collaborative Agreements Language

The agent(s) supplied by CTEP, DCTD, NCI used in this protocol is/are provided to the NCI under a Collaborative Agreement (CRADA, CTA, CSA) between the Pharmaceutical Company(ies) (hereinafter referred to as "Collaborator(s)") and the NCI Division of Cancer Treatment and Diagnosis. Therefore, the following obligations/guidelines, in addition to the provisions in the "Intellectual Property Option to Collaborator" ([http://ctep.cancer.gov/industryCollaborations2/intellectual\\_property.htm](http://ctep.cancer.gov/industryCollaborations2/intellectual_property.htm)) contained within the terms of award, apply to the use of the Agent(s) in this study:

1. Agent(s) may not be used for any purpose outside the scope of this protocol, nor can Agent(s) be transferred or licensed to any party not participating in the clinical study. Collaborator(s) data for Agent(s) are confidential and proprietary to Collaborator(s) and shall be maintained as such by the investigators. The protocol documents for studies utilizing Agents contain confidential information and should not be shared or distributed without the permission of the NCI. If a copy of this protocol is requested by a patient or patient's family member participating on the study, the individual should sign a confidentiality agreement. A suitable model agreement can be downloaded from: <http://ctep.cancer.gov>.
2. For a clinical protocol where there is an investigational Agent used in combination with (an)other Agent(s), each the subject of different Collaborative Agreements, the access to and use of data by each Collaborator shall be as follows (data pertaining to such combination use shall hereinafter be referred to as "Multi-Party Data"):
  - a. NCI will provide all Collaborators with prior written notice regarding the existence and nature of any agreements governing their collaboration with NCI, the design of the proposed combination protocol, and the existence of any obligations that would tend to restrict NCI's participation in the proposed combination protocol.
  - b. Each Collaborator shall agree to permit use of the Multi-Party Data from the clinical trial by any other Collaborator solely to the extent necessary to allow said other Collaborator to develop, obtain regulatory approval or commercialize its own Agent.
  - c. Any Collaborator having the right to use the Multi-Party Data from these trials must agree in writing prior to the commencement of the trials that it will use the Multi-Party Data solely for development, regulatory approval, and commercialization of its own Agent.
3. Clinical Trial Data and Results and Raw Data developed under a Collaborative Agreement will be made available to Collaborator(s), the NCI, and the FDA, as appropriate and unless additional disclosure is required by law or court order as described in the IP Option to

Collaborator ([http://ctep.cancer.gov/industryCollaborations2/intellectual\\_property.htm](http://ctep.cancer.gov/industryCollaborations2/intellectual_property.htm)). Additionally, all Clinical Data and Results and Raw Data will be collected, used and disclosed consistent with all applicable federal statutes and regulations for the protection of human subjects, including, if applicable, the *Standards for Privacy of Individually Identifiable Health Information* set forth in 45 C.F.R. Part 164.

4. When a Collaborator wishes to initiate a data request, the request should first be sent to the NCI, who will then notify the appropriate investigators (Group Chair for Cooperative Group studies, or PI for other studies) of Collaborator's wish to contact them.
5. Any data provided to Collaborator(s) for Phase 3 studies must be in accordance with the guidelines and policies of the responsible Data Monitoring Committee (DMC), if there is a DMC for this clinical trial.
6. Any manuscripts reporting the results of this clinical trial must be provided to CTEP by the Group office for Cooperative Group studies or by the principal investigator for non-Cooperative Group studies for immediate delivery to Collaborator(s) for advisory review and comment prior to submission for publication. Collaborator(s) will have 30 days from the date of receipt for review. Collaborator shall have the right to request that publication be delayed for up to an additional 30 days in order to ensure that Collaborator's confidential and proprietary data, in addition to Collaborator(s)'s intellectual property rights, are protected. Copies of abstracts must be provided to CTEP for forwarding to Collaborator(s) for courtesy review as soon as possible and preferably at least three (3) days prior to submission, but in any case, prior to presentation at the meeting or publication in the proceedings. Press releases and other media presentations must also be forwarded to CTEP prior to release. Copies of any manuscript, abstract and/or press release/ media presentation should be sent to:

Email: [[contact]](mailto:[contact])

The Regulatory Affairs Branch will then distribute them to Collaborator(s). No publication, manuscript or other form of public disclosure shall contain any of Collaborator's confidential/proprietary information.

## 12.5 Genomic Data Sharing Plan

*If genomic data will be studied, analyzed, collected, and stored in an NIH/NCI Genomic Data Biorepository (e.g., dbGaP, Cancer Genomic Database, other), please describe the genomic data sharing plan for this trial. Please refer to the NCI Genomic Data Sharing Policy at <http://www.cancer.gov/grants-training/grants-management/nci-policies/genomic-data> for considerations regarding the sharing of data, protection of patient confidential information, and the provision of adequate information in the patient informed consent.*

## 13. STATISTICAL CONSIDERATIONS

### 13.1 Study Design/Endpoints

Primary Endpoint:

To determine the dose limiting toxicities and maximum tolerated dose of TALIMOGENE LAHERPAREPVEC in combination with chemotherapy and radiation in rectal cancer

Study Design:

Chemoradiation will be at current standard of care doses i.e. 50.4 Gy over 28 fractions in combination with capecitabine 825 mg/m^2 po bid, days of radiation only (M-F). TALIMOGENE LAHERPAREPVEC will be escalated in 2 dose levels (PFU /ml) as indicated below using a standard 3 + 3 design.

- Talimogene laherparepvec will be administered via endoscopy by a qualified physician for a total of 4 doses at the following time points: a) week 1 prior to initiation of FOLFOX chemotherapy b) weeks 2-4 during FOLFOX chemotherapy c) week 6 d) week 8-9 during chemoradiation
- The first cohort of 3 patients will be treated at dose level 1.
- The next cohort of patients will not be treated until toxicity has been evaluated in the current cohort of patients.
- The algorithm is as follows: (1) If 0 out of 3 patients experiences dose-limiting toxicity (DLT), the next cohort of 3 patients will be treated at the next higher dose level. (2) If 1 out of 3 patients develops DLT, additional 3 patients will be treated at the same dose level. If no more DLT develops at the dose, i.e. 1 out of a total of 6 patients develops DLT, the dose escalation continues to next higher level for a cohort of 3 patients. (3) At any given dose, if more than 1 out of 3 patients or 6 patients experience DLT, the dose level exceeds the MTD and 3 patients will be treated at the next lower dose level if there are less than 6 patients already treated at that dose. If this is the lowest dose level tested, the trial will be terminated and MTD is not found. Following the above algorithm, MTD is defined as the highest dose level in which 6 patients have been treated with at most 1 instance of DLT

Dose level	TALIMOGENE LAHERPAREPVEC Dose (PFU/ml)	Capecitabine (mg/m  po bid on days of radiation)	Radiation
1	10  , 10  , 10  , 10 	825	50.4 gray in 28 fractions
2	10  , 10  , 10  , 10 	825	50.4 gray in 28 fractions

Based on the 3+3 design, the MTD is defined as the highest dose level in which 6 patients have been treated with at most 1 instance of DLT. Thus the target DLT rate is <=16.7%. The study only includes two dose levels, and the following table shows the operating characteristics of the 3+3 design under four different scenarios. For each scenario, the % time selecting a dose as the MTD, the average sample size treated at each dose level, and the probability of stopping the trial early are presented.

Scenario	Doses	1	2
#1	Trued DLT	0.10	0.17
	% MTD	21%	70%
	Average # patients	3.7	3.7
	Prob(early stopping)	0.1	
#2	Trued DLT	0.10	0.25
	% MTD	36%	57%
	Average # patients	3.8	3.9
	Prob(early stopping)	0.08	
#3	Trued DLT	0.40	0.50
	% MTD	26%	5%
	Average # patients	4.3	1.3
	Prob(early stopping)	0.69	
#4	Trued DLT	0.05	0.10
	% MTD	9%	88%
	Average # patients	3.4	3.6
	Prob(early stopping)	0.02	

Given the novelty and complexity of this study, a review of the data with the sponsor will occur before initiation of new dose levels. A total of 15 patients will be treated at the MTD (including the 6 from dose escalation phase and an addition 9 patients in expansion cohort) to assess safety of this dose level. Up to 15 patients (including the 6 patients treated at the MTD during dose escalation) will be enrolled into the expansion cohort to further confirm the safety of the MTD (as described in the study primary objective) and to assess efficacy and biomarker change (as described in the study secondary & exploratory objectives). With a total sample size of 15 and assuming the true DLT rate is 0.167, then the probability of observing at least one DLT event is 93.5%. If the true DLT rate is 0.30, then the probability of observing at least one DLT event is 99.5%. The MTD will be deemed to be recommended phase II dose (RP2D) if  $\geq 80\%$  of the patients are able to receive  $\geq 80\%$  of the planned treatment doses. If  $\geq 1/3$  of all patients at this dose experience DLTs, enrollment will be stopped and the Principal Investigator will discuss with all study investigators and with CTEP whether further addition of patients is needed to re-assess the RP2D. Monitoring of all safety and toxicity data is done by the Principal Investigator and the Corresponding Organization on a real-time basis as data are entered into Medidata Rave using the Web Reporting Module.

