### 13.2 Sample Size/Accrual Rate

At least 2 patients and no more than 21 patients will be accrued onto this trial. Based on our prior experience, we estimate to identify 2-3 eligible patients per month.

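### Section 13.1 still gives the pre-amendment design and a table that does not follow the six-at-the-MTD rule, and nothing says whether long-course level 1 patients count at level 1 (amended)

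*Combined protocol and SAP*

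**What the plan says.** Section 13.1 sets the radiation backbone as "Chemoradiation will be at current standard of care doses i.e. 50.4 Gy over 28 fractions in combination with capecitabine", and its dose table repeats that backbone at both levels. It places the last two injections at "c) week 6 d) week 8-9 during chemoradiation". It also says "TALIMOGENE LAHERPAREPVEC will be escalated in 2 dose levels (PFU /ml) as indicated below" and "The study only includes two dose levels".

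The Schema, Section 2.4 and the dose table in Section 5.1 (headed as amended) differ. They mark long-course level 1 as completed, give level 2 with 25 Gy in 5 fractions and no capecitabine, and add a third row, level 1 (amended), to be used if DLTs are seen at level 2. Injections move to weeks 3, 5 and 7 after the first. The Section 10 calendar agrees. Section 2.4 presents the Section 13.1 regimen and timing as the way the trial was started, and reports that the first cohort had no DLTs.

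On counting, Section 13.1 says "3 patients will be treated at the next lower dose level if there are less than 6 patients already treated at that dose". The Section 5.2 table adds three only where exactly three were treated before. Both sections want six patients at the MTD, with at most one DLT. Sections 5.3 and 13.1 fix 15 at the MTD, and a second sentence in 13.1 makes 15 an upper limit. Section 13.2 says "At least 2 patients and no more than 21 patients will be accrued onto this trial".

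**The concern.** The MTD is the primary endpoint, and Section 13.1 is operative text, not a change log. Read alone, it describes a trial that the treatment sections no longer run, so its table cannot support the amended path.

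The amendment also left a gap. Level 1 (amended) has the same virus concentrations as long-course level 1 but different radiation and injection timing. If level 2 is not accepted, someone must decide whether the earlier patients count toward the six. If they do, three new patients complete the level. If not, six are needed: the Section 5.2 trigger is then not met, because no one was treated there before, and the Section 13.1 rule enters the first three of the six. A choice made after the level 2 results would be post hoc, and it affects both the chance of declaring an MTD and the total sample size.

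**Working it through.** **Inputs.** DLT scenarios, selection percentages and averages: Section 13.1 table. Six at the MTD with at most one DLT: Sections 5.2 and 13.1. Fifteen at the MTD: 5.3 and 13.1. Cap of 21: 13.2. Long-course cohort: assumed to be three patients (13.1 plans "The first cohort of 3 patients will be treated at dose level 1"; 2.4 gives no number) with no DLTs (2.4).

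**1. The plan's own figures.** The cap fits 6 + 15 = 21, although the document does not show this. At least one DLT in 15: 1 − 0.833^15 = 93.5% and 1 − 0.7^15 = 99.5%. Both match Section 13.1.

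**2. The table.** It reports "the average sample size treated at each dose level". Let A be the chance of clearing level 1 (0/3, or 1/3 then 0/3) and p the level 2 DLT rate.

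- Without filling: selection = A × [P(0/3) + P(1/3)P(0/3)]; average at level 2 = A × [3 + 3P(1/3)].
- Filled to six: selection = A × P(≤1/6); average = A × [6 − 3P(≥2/3)].

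Scenario 1: A = 0.729 + 0.243 × 0.729 = 0.906. Unfilled: 0.906 × 0.773 = 70.0%, average 0.906 × (3 + 3 × 0.351) = 3.67. Filled: 0.906 × 0.729 = 66.0%, average 0.906 × (6 − 3 × 0.077) = 5.23.

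| Scenario (DLT rates, levels 1/2) | Level 2 average: stated / unfilled / filled | Level 2 selected: stated / unfilled / filled |
|---|---|---|
| 1 (10/17%) | 3.7 / 3.67 / 5.23 | 70% / 70.0% / 66.0% |
| 2 (10/25%) | 3.9 / 3.87 / 5.01 | 57% / 54.4% / 48.4% |
| 3 (40/50%) | 1.3 / 1.28 / 1.39 | 5% / 5.3% / 3.4% |
| 4 (5/10%) | 3.6 / 3.63 / 5.76 | 88% / 88.2% / 86.2% |

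The stated averages follow the unfilled rule. The 57% in scenario 2 matches neither calculation exactly and may be simulation error.

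**3. When the counting gap applies.** Only if level 2 is not accepted. Filled to six, that is 1 − P(≤1/6). Level 1 (amended) is then accepted with probability P(≤1/6) if the long-course patients do not count, or P(≤1/3) on three new patients if three DLT-free ones do. The effect over all trials is the product of the first column and the difference between the next two.

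| DLT rates (levels 1/2) | Level 2 not accepted | Accepted, not counted | Accepted, counted | Change in finding an MTD |
|---|---|---|---|---|
| 5/10% | 11.4% | 96.7% | 99.3% | 0.3 points |
| 10/17% | 27.1% | 88.6% | 97.2% | 2.3 points |
| 10/25% | 46.6% | 88.6% | 97.2% | 4.0 points |
| 40/50% | 89.1% | 23.3% | 64.8% | 37 points |

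At a 30% rate, which is not a level 1 scenario in the plan: 0.7^6 + 6 × 0.3 × 0.7^5 = 42.0% not counted, against 0.343 + 0.441 = 78.4% counted.

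**4. The cap**, with three long-course patients and no replacements:

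- Level 2 accepted: 3 + 15 = 18.
- Counted, level 1 (amended) is the MTD: at most 3 + 6 + 12 = 21.
- Not counted, level 2 fails in its first cohort: at most 3 + 3 + 15 = 21.
- Not counted, level 2 fails in its second cohort (at its 4th, 5th or 6th patient): 3 + 4 + 15 = 22 up to 3 + 6 + 15 = 24.

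The last path has probability P(fails in second cohort) × P(≤1/6) = 8.3%, 17.2%, 27.4% and 9.1% in the row order above, before any early stop in the expansion.

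**5. Holding 21 on that path** leaves 21 − 3 − 6 = 12 at the MTD. At least one DLT: 1 − 0.833^12 = 88.8% and 1 − 0.7^12 = 98.6%.

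**The case against.** A reader might infer that the plan does not say how many patients level 1 (amended) needs. It does: six with at most one DLT. Only the status of the earlier patients is open. Entering three and then three more is ordinary 3+3 practice, not a conflict.

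The gap between 42% and 78% is tempting as a headline, but it is conditional on level 2 failing and uses a 30% rate. In the three plausible scenarios the unconditional effect is 4 points or less. The 37-point case (40/50%) is hard to credit after a DLT-free long-course cohort.

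Nor is a breach of the cap certain. Sections 5.3 and 13.1 stop enrollment if one third or more of the patients at the dose have DLTs. Checked after each patient from the seventh (an assumption), this lowers the 40/50% figure from 9.1% to about 5% and barely moves the others. If 15 is only an upper limit, 21 can be kept.

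The separate row, the completed status of long-course level 1 and the changed injection weeks lean toward not counting. Identical concentrations and the statement of two levels lean the other way, though that statement sits in the unreconciled text. This lean is not a rule. Section 13.1 requires review with the sponsor before new dose levels, and Section 12.1 requires principal investigator sign-off on de-escalation. These make an unnoticed decision less likely but supply no criterion.

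Finally, one might infer that sites would give the wrong regimen. Section 5.1 is headed as amended and agrees with the calendar, so the documents do not support that.

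**Conclusion.** This is an internal inconsistency that should be fixed. It does not undermine the trial. Two parts are wrong as written, whatever the counting rule: Section 13.1 contradicts the Schema and Sections 2.4, 5.1 and 10, and its table ignores filling to six, which overstates selection of level 2 by about 2 to 9 points.

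The third part is an omission with a limited effect. It applies only if level 2 is not accepted, and then changes whether an MTD is found in about 0.3, 2.3 and 4.0 of 100 trials at rates of 5/10%, 10/17% and 10/25%. The conflict between 15 and 21 arises on one path only: long-course patients not counted, level 2 failing in its second cohort, 15 read as fixed, and no early stop. These sizes assume three DLT-free long-course patients, no replacements, and level 2 filled to six.

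**What to change.** - Reconcile Section 13.1 with the Schema and Sections 2.4, 5.1 and 10 on regimen, injection times and number of levels.
- Before level 2 results are known, state whether long-course level 1 patients count at level 1 (amended). Report DLTs by regimen either way.
- Recalculate the operating-characteristics table for the amended path, with filling to six and de-escalation applied.
- Make the two statements about 15 patients agree with each other and with the cap. If 21 is kept, state 12 to 15 at the MTD, with an 88.8% to 93.5% chance of at least one DLT at a 16.7% rate and 98.6% to 99.5% at 30%. Otherwise state the higher maximum and revise the enrollment table.
- Reconcile the de-escalation wordings in Sections 5.2 and 13.1 with the dose-table note that brings in level 1 (amended) when DLTs are seen at level 2. Under the 3+3 rule, one DLT in three expands level 2.

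Cost: wording in Sections 5.2, 5.3, 13.1 and 13.2 and the dose-table notes, plus one short recalculation. Keeping 21 adds no patients but gives a slightly less favourable detection probability on one path. The higher maximum adds up to three patients.

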### **AEs that are considered “Dose Limiting” for talimogene laherparepvec**

- 1) Herpetic events that should be considered DLTs:
  - Serious herpetic events such as herpetic encephalitis, encephalomyelitis or disseminated herpetic infection

- Any herpetic events confirmed due to talimogene laherparepvec that require treatment with acyclovir or similar anti-viral agent. Talimogene laherparepvec treatment should be held if systemic acyclovir or other anti-viral is indicated. If ongoing anti-viral treatment is required, talimogene laherparepvec treatment should be permanently discontinued
  - \* Herpetic events due to wild-type HSV-1 or wild-type HSV-2 which require acyclovir and are not due to talimogene laherparepvec (as confirmed by PCR testing) should not be considered as DLTs caused by talimogene laherparepvec.

2) DLT will also be defined as any of the following talimogene laherparepvec-related toxicity:

- Grade 2 or greater immune-mediated AEs.
- Grade 2 or greater allergic reactions.
- Any grade plasmacytoma
- Any other grade 3 or greater hematologic or non-hematologic toxicity, with the exceptions of:
  - any grade of alopecia,
  - grade 3 arthralgia or myalgia,
  - brief (< 1 week) grade 3 fatigue,
  - grade 3 fever,
  - grade 3 diarrhea or vomiting responding to supportive care.

For other study treatments, DLT will be defined as clinically significant (ie excluding any grade alopecia, grade 3 arthralgia or myalgia, < 1 week grade 3 fatigue, grade 3 diarrhea, nausea, vomiting responding to supportive care), grade 3 or 4 toxicities possibly or probably related to study treatment or AEs.

Management and dose modifications associated with the above adverse events are outlined in Section 6.

Dose escalation will proceed within each cohort according to the following scheme. Dose-limiting toxicity (DLT) is defined above.

Number of Patients with DLT at a Given Dose Level	Escalation Decision Rule
0 out of 3	Enter 3 patients at the next dose level.
≥2	Dose escalation will be stopped. This dose level will be declared the maximally administered dose (highest dose administered). Three (3) additional patients will be entered at the next lowest dose level if only 3 patients were treated previously at that dose.

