1 out of 3	Enter at least 3 more patients at this dose level. 

• If 0 of these 3 patients experience DLT, proceed to the next dose level.

• If 1 or more of this group suffer DLT, then dose escalation is stopped, and this dose is declared the maximally administered dose. Three (3) additional patients will be entered at the next lowest dose level if only 3 patients were treated previously at that dose.

≤1 out of 6 at highest dose level	This is generally the maximum tolerated dose, MTD. At least 6 patients must be entered at the MTD.

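### The operating-characteristics table in Section 13.1 does not describe the plan's six-patient MTD rule: in Scenarios 1, 2 and 4 the level 2 averages are lower than the table's own selection rates allow

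*Combined protocol and SAP*

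**What the plan says.** Section 13.1 states that "the MTD is defined as the highest dose level in which 6 patients have been treated with at most 1 instance of DLT", and then that "the following table shows the operating characteristics of the 3+3 design under four different scenarios". The table gives selection rates, average numbers treated per level and early-stopping probabilities for four pairs of true DLT rates.

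Other passages support six patients at the MTD:

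- The escalation rule table in Section 5.2: "At least 6 patients must be entered at the MTD".
- The expansion paragraph of Section 13.1, which counts 15 patients at the MTD, "including the 6 from dose escalation phase and an addition 9 patients in expansion cohort".

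If level 2 fails, level 1 is filled. Section 13.1 has "3 patients will be treated at the next lower dose level if there are less than 6 patients already treated at that dose", and Section 5.2 has "Three (3) additional patients will be entered at the next lowest dose level if only 3 patients were treated previously at that dose".

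Section 13.1 also still describes the pre-amendment path (50.4 Gy plus capecitabine): "The first cohort of 3 patients will be treated at dose level 1". The Schema, Section 2.4 and the dose table in Section 5.1 describe that level as completed, with no DLTs. They put level 2 next, on short-course radiation, with an amended level 1 as fallback.

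**The concern.** Level 2 is selected in 70% and 88% of trials in Scenarios 1 and 4, yet the average number treated there is 3.7 and 3.6. That cannot be so if every selection of level 2 needs six patients.

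Finding the MTD is the primary objective, and this table is where the plan reports how often each level would be chosen. If it was computed for another rule, the plan's stated ability to find the MTD and its expected escalation size are not those of the design it specifies.

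**Working it through.** **Inputs (Section 13.1 table).** Level 1 / level 2 in each pair.

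| Scenario | True DLT rate | % MTD | Average n | Early stopping |
|---|---|---|---|---|
| 1 | 0.10 / 0.17 | 21 / 70 | 3.7 / 3.7 | 0.1 |
| 2 | 0.10 / 0.25 | 36 / 57 | 3.8 / 3.9 | 0.08 |
| 3 | 0.40 / 0.50 | 26 / 5 | 4.3 / 1.3 | 0.69 |
| 4 | 0.05 / 0.10 | 9 / 88 | 3.4 / 3.6 | 0.02 |

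Each scenario's two selection rates and early-stopping value sum to 0.99 to 1.01, so early stopping is read here as no MTD found.

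**Step 1. Reproduce the printed table.** Take full cohorts of three, accept level 2 after 0/3 or 1/6, and fill neither level to six. Let R = (1−p1)³ + 3p1(1−p1)⁵ be the chance of reaching level 2, and B = (1−p2)³ + 3p2(1−p2)⁵. Then level 2 is selected with probability R×B, level 1 with R×(1−B), and no MTD is found with 1−R. The mean at level 2 is R×[3 + 3×P(exactly 1 of 3)].

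Scenario 1: R = 0.729 + 0.177 = 0.906 and B = 0.572 + 0.201 = 0.773, so level 2 selection is 70.0%. The mean is 0.906×(3 + 3×0.351) = 3.67.

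| Scenario | Level 2 % | Level 1 % | No MTD | Mean level 1 | Mean level 2 |
|---|---|---|---|---|---|
| 1 | 70.0 | 20.6 | 0.094 | 3.73 | 3.67 |
| 2 | 54.4 | 36.3 | 0.094 | 3.73 | 3.87 |
| 3 | 5.3 | 25.6 | 0.691 | 4.30 | 1.28 |
| 4 | 88.2 | 9.1 | 0.027 | 3.41 | 3.63 |

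At printed precision 16 of 20 cells match. The exceptions are Scenario 2 level 2 selection, level 1 mean and early stopping, and Scenario 4 early stopping.

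**Step 2. Lower bound from the printed figures alone.** Under the six-patient rule, mean at level 2 ≥ 6×(% level 2) + 3×(% level 1).

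- Scenario 1: 6(0.70) + 3(0.21) = 4.83, printed 3.7.
- Scenario 2: 6(0.57) + 3(0.36) = 4.50, printed 3.9.
- Scenario 3: 6(0.05) + 3(0.26) = 1.08, printed 1.3 (no conflict).
- Scenario 4: 6(0.88) + 3(0.09) = 5.55, printed 3.6.

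The plan does not say whether a cohort is completed after a second DLT, and Section 13.2 ("At least 2 patients and no more than 21 patients will be accrued onto this trial") suggests it may not be. Replacing the 3 by 2 gives 4.62, 4.14 and 5.46 in Scenarios 1, 2 and 4, still above the printed values. In the closest case, Scenario 2, allowing for rounding gives at least 6(0.565) + 2(0.355) = 4.10, against at most 3.95.

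**Step 3. Exact values for the rule as written.** Let A(p) = (1−p)⁶ + 6p(1−p)⁵, the chance of at most 1 DLT in 6. Level 2 is selected with probability R×A(p2), level 1 with A(p1)×[1−A(p2)], and no MTD is the remainder. With full cohorts the mean at level 2 is R×[3 + 3×P(at most 1 of 3)].

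Scenario 1: A(0.17) = 0.729, so level 2 selection is 0.906×0.729 = 66.0%. The mean is 0.906×(3 + 3×0.923) = 5.23.

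| Scenario | Level 2 % | Level 1 % | No MTD | Mean level 1 | Mean level 2 | Total |
|---|---|---|---|---|---|---|
| 1 | 66.0 | 24.0 | 0.099 | 4.32 | 5.23 | 9.55 |
| 2 | 48.4 | 41.3 | 0.103 | 4.75 | 5.01 | 9.76 |
| 3 | 3.4 | 20.8 | 0.758 | 4.87 | 1.39 | 6.27 |
| 4 | 86.2 | 11.1 | 0.027 | 3.70 | 5.76 | 9.46 |

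Only 1 of 20 printed cells matches (Scenario 1 early stopping, printed as 0.1). If a cohort stops at two DLTs, the probabilities are unchanged and the totals become 9.27, 9.33, 5.39 and 9.35. The printed means sum to 7.4, 7.7, 5.6 and 7.0.

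**Step 4. Separate the rule from simulation error.** Between steps 1 and 3, level 2 selection falls by 4.0, 6.0, 1.9 and 2.0 points. The other 2.6 points in Scenario 2 (57 printed, 54.4 exact) may be simulation error. The plan gives no number of runs; for an assumed 500 to 2,000, the standard error √(0.544×0.456/n) is 2.2 to 1.1 points.

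**The case against.** The arithmetic is hard to dispute, but four points can be made in the table's favour.

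- **The numbered algorithm has no step adding three patients at level 2 after 0/3.** Followed literally, it gives all four printed level 2 averages. This probably explains the error. It does not excuse it, because the same section's MTD definition and Section 5.2 require six.
- **The six could be expansion patients.** Section 5.3 attributes the 6 to dose expansion. That looks like a slip: the parallel paragraph in Section 13.1 assigns them to escalation and counts 9 more in expansion.
- **Early stopping could mean failing level 1 at the first pass.** The printed 0.69 in Scenario 3 is then right, and 2 of 20 cells match the written rule instead of 1. The row sums favour the reading used here. The level 2 averages fail on either reading.
- **The first cohort is done, so the unconditional figures no longer describe what remains.** This stands in part. On the path now in force, level 2 selection is 73/53/11/89%, so the printed values are too low in three of four scenarios. The overstatement applies to the rule as Section 13.1 writes it, and a table for the current path would not be uniformly less favourable.

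It is also true that no decision rule uses the table. When level 2 is the MTD, the three extra patients are already within the planned 15.

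**Conclusion.** The concern holds: the table is wrong for the rule the plan states. In Scenarios 1, 2 and 4 the contradiction follows from the printed numbers alone and survives rounding, simulation error and either assumption about completing cohorts. Scenario 3 does not breach the bound.

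Against the written rule, the rule mismatch overstates level 2 selection by about 2 to 6 points. In Scenario 3, where both levels are toxic, level 1 selection is overstated (26% against 21%) and the chance of no MTD understated (0.69 against 0.76, reading early stopping as no MTD). Total escalation size is understated by about 1.6 to 2.5 patients in Scenarios 1, 2 and 4. In Scenario 3 the direction depends on whether cohorts are completed.

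The effect is on the reported performance for the primary endpoint and on expected escalation size, not on enrolment at the MTD. It should be corrected, but it does not invalidate the design.

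**What to change.** 1. Reconcile Section 13.1 with the Schema, Section 2.4 and Section 5.1. Two points are open: whether the completed 0/3 at pre-amendment level 1 counts towards six, and what triggers the fallback. Sections 5.2 and 13.1 use two or more DLTs, while the dose tables refer only to DLTs being noted at level 2.
2. Add the top-up to six after 0/3 at level 2 to the numbered algorithm, so that it agrees with the MTD definition. State whether a cohort is completed after a second DLT, and define the early-stopping row.
3. Replace the table once with exact values for the path in force, labelled as conditional on having cleared level 1. Give a range for any point still open.

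As an illustration only, assume fallback at two or more DLTs and the scenario's level 1 rate at amended level 1. Level 2 is then selected in 73/53/11/89% of trials.

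| | Level 1 selected, Scenarios 1/2/3/4 | No MTD |
|---|---|---|
| The 0/3 counts | 26/45/58/11% | 0.01/0.01/0.31/<0.01 |
| It does not | 24/41/21/11% | 0.03/0.05/0.68/<0.01 |

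The cost is about an hour of enumeration and one replaced table, once the open points are settled. Like for like, the selection figures become slightly less favourable.
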